## Purpose

This study is designed to test the efficacy of a novel electrical stimulation platform named the Tennant Biomodulator designed by AVAZZIA to accelerate wound healing, reduce pain and improve mobility in patients with diabetes and lower extremities ulcers/wounds after four weeks of therapy. In addition,

The objective of the study is to examine effectiveness of transcutaneous electrical stimulation (TENS) as an adjunct therapy to improve wound outcomes among people with plantar ulcers. Our hypotheses are:

H1: TENS is effective to relieve pain in particular during night and during dressing change

H2: TENS is effective to increase skin perfusion

H3: TENS is effective to speed up wound healing weekly rate

H4: TENS is effective to improve mobility :

**Table I: Patient Population**

Inclusion Criteria	
Able to provide informed consent
 
18-85 years old
 
Clinically confirmed diabetes (ADA criteria)
 
One or more active non-infected lower extremities ulcer or wound
 
Subject or responsible caregiver is willing and to maintain the required offloading (as applicable the location of the ulcer) and applicable dressing changes and electrical stimulation application.

Exclusion Criteria	
Subject has a demand-type cardiac pacemaker, implanted defibrillator or other implanted electronic device
 
Is pregnant
 
Is nursing or actively lactating
 
Has history of seizures.
 
Active wound infection
 
Active Charcot Foot
 
Non-ambulatory (Unable to walk 40 feet with or without assistive device)
 
Bilateral AK/BK amputation
 
Active drug/alcohol abuse (or history in the last year)
 
Dementia or severe cognitive impairment
 
Subjects with excessive lymphedema
 
Subjects with osteomyelitis and/or gangrene
 
Unable to comply with research appointments (e.g. long travel)

	
Wide spread malignancy or systemically immunocompromising disease
 
Subject has a history of or any intercurrent illnesses or conditions that would compromise the safety of the subject according to judgement of a qualified wound specialist.

--	--

## Background

Electrical stimulation may offer a unique treatment option to heal complicated and recalcitrant wounds, improve flap and graft survival, and even reduce the likelihood of ulceration. Electrical stimulation has been suggested to reduce infection, improve cellular immunity, increase perfusion, relieve pain, improve plantar sensation, and accelerate wound healing. At least five studies reported significant benefit of electrical stimulation on perfusion as measured by different tools able to measure cutaneous perfusion including laser Doppler flowometry, microvessel density, and measures of transcutaneous oxygen. While previous studies revealed that electrical stimulation could be effective to accelerate wound healing, prior studies limited to in-clinic and supervised use of electrical stimulation therapy and to our knowledge there is no randomized controlled trial examining potential benefit of in-home and daily use of electrical stimulation to accelerate wound healing.

Normal wound healing consists of regulated and integrated phases: hemostasis, inflammation, proliferation and tissue re-modelling. Oxygen plays a central role in each step of the healing process. Poor tissue perfusion caused by peripheral arterial disease (PAD) is highly prevalent among people with diabetes and interrupts this normal process by creating a system of localized hypoxia. PAD has its effects on the local wound environment by macro-vascular and microvascular processes. Macro-vascular disease is the sequelae of atherosclerosis on larger axial vessels. The earliest vascular change here begins with intimal thickening, which consists of increased smooth muscle cells and abnormal deposits of extracellular matrix within the tissue. Initially, blood flow is minimally affected but as the disease progresses there is increased disruption of flow and consequently the creation of an ischemic environment. Unlike ulceration from venous insufficiency, where disease usually arises in the distal leg or so called “gaiter” regions, arterial leg wounds typically affect the forefoot or toes, though wounds present at any spot distal to the arterial perfusion abnormality may suffer from non-healing regardless of original etiology. A compounding factor common in patients with diabetes is the effect of compromised mobility on their disease process. Diminished mobility can lead to prolonged periods of unrelieved pressure on the extremities resulting in increased shearing force applied to the skin and underlying tissues leading to a decrease in oxygen tension and eventual tissue necrosis.

Electrical stimulation could have positive effect on not only increasing skin perfusion in people with diabetes but also could improve mobility and balance via enhancing plantar sensation as demonstrated in our recent study. Thus, plantar stimulation not only may be beneficial to accelerate wound healing in people with diabetes but also may assist to improve mobility and reduce the likelihood of recurrence of ulcers. In this study, we proposed to examine effectiveness of daily home use of an innovative portable electrical stimulation platform (Tennant Biomodulator by AVAZZIA) to accelerate wound healing in people with diabetes. We

hypothesize that daily use of the Tennant Biomodulator for 4 consecutive weeks is effective to increase skin perfusion, accelerate wound healing, and improve balance and mobility in people with diabetes and plantar ulcers or wounds.

## Study Design

We are proposing a clinical study at the Baylor College of Medicine, Division of Vascular Surgery and Endovascular Therapy, to test the efficacy of daily home use of a novel electrical stimulation platform named the Tennant Biomodulator designed by AVAZZIA to accelerate wound healing, relieve pain and improve mobility in people with diabetes and non-infected plantar ulcers or wounds. In addition, we will examine immediate benefit of electrical stimulation provided by the Tennant Biomodulator on increasing skin perfusion. Our specific aims are:

**Aim1: Examine immediate benefit of lower extremity electrical stimulation to improve tissue perfusion (short term benefit):** We will recruit 40 eligible subjects (see table I for eligibility criteria). They will receive lower extremity electrical stimulation (at the shin level) for duration of approximately one hour using the Tennant Biomodulator Pro device. Skin perfusion before, at mid-point (approximately 30 min) and at the end of therapy will be measured. Skin perfusion will be assessed by Skin Perfusion Pressure (Sensilase, Vasamed Inc, MN, USA) and Kent Imaging. Other modalities such as HyperView Imaging (HyperMed Imaging, Inc., TN, USA) may be also used as comparator. Our hypothesis is:

*H1:* One-hour use of lower extremity electrical stimulation therapy will increase tissue perfusion.

**Aim2: Examine long-term benefit of daily home use of lower electrical stimulation (long-term benefit):** Eligible participants will be randomized (ratio: 1:1) to either active (active group, n=20) or sham (sham group, n=20) therapy group. After receiving education, both groups will receive a home-based electrical stimulation system (Tennant Biomodulator device) for daily use at home up to 4 weeks. The duration of each treatment session per day will be one hour. The active group will receive an active electrical stimulation device. The control group will receive an identical device but without active electrical stimulation output. Participants and physicians who are treating the wound would be blinded to the type of device assignment. The study coordinator will be aware of assignment (active device or sham device). Each unit will be coded with a unique identification number. At the last visit, the study coordinator will reveal their group allocation. Since participating patients will have moderate-to-severe peripheral sensory neuropathy, they will be unable to determine via “feeling” whether or not they were receiving electrical stimulation. Patients will visit the clinic on weekly basis up to 4 weeks for assessing outcomes. The primary outcomes include changes in speed of wound healing and changes in plantar sensation. Secondary outcomes include patients self-report outcomes (e.g., pain, sleep quality, and quality of life), changes in mobility (e.g. physical activities and gait), and adverse outcomes (e.g., infection, amputation, etc.). Skin perfusion will be assessed similar to the method described in the Aim 1. Plantar sensation will be assessed using vibratory

perception threshold. Balance will be assessed using wearable sensors (BalanSENS, Biosensics LLC, MA, USA), mobility will be assessed using wearable sensors (PAMSys, Biosensics LLC, MA, USA), sleep quality will be assessed using PSQI questionnaire, and quality of life will be assessed using PROMIS Global.

Our hypotheses are

*H2:* Weekly speed of wound healing would be higher in the active group compared to the shame group

*H3:* Plantar sensation is improving in the active group in response to active therapy.

*H4:* Patient-reported outcomes and other secondary outcomes will be improved in the active group.

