## **Study Device**

BEST™ (Bio-Electric Stimulation Technology) devices produce unique microcurrent impulses transmitted through the skin to interface with the internal peripheral nervous system for the purpose of therapeutic intervention. The BEST microcurrent output stimulation is a train of high-voltage, pulsed-current, damped, sinusoidal and asymmetrical pulses. BEST devices react to the body's response to the microcurrent stimulus. With each response, the electrical properties of the tissue change. These changes in the tissue characteristics result in changes in the output. The device detects changes and indicates relative tissue reaction responses in a cybernetic feedback loop. BEST products are controlled by a high-performance microcomputer chip, which uses Avazzia proprietary software. These hand-held devices are FDA-cleared for the symptomatic relief and management of chronic, intractable pain and adjunctive treatment in the management of post-surgical and post-traumatic pain (available by prescription). These non-invasive neuro-stimulation devices allow patients to take control of their pain management. Avazzia BEST products feature a tissue reaction response indication, making them superior to traditional TENS units. BEST products work on different neural paths than a traditional TENS.

Avazzia BEST device technology and modes including the Tennant Biomodulator® devices have been FDA-cleared as transcutaneous electro-nerve stimulators for pain relief since 2007.

- K062641 clearance for BEST-AV1 family of micro current Rx devices with LED display for pain relief including reaction technology. The Tennant Biomodulator® device is a BEST-AV1 device. These devices are cleared for symptomatic relief and management of chronic, intractable pain, and adjunctive treatment in the management of post-surgical and post-traumatic pain (prescription required).
- K123099 clearance for BEST-AV2 professional family of Rx devices with LCD displays for pain relief including reaction technology. The Tennant Biomodulator PRO® device is a BEST-AV2 device. The difference between BEST-AV1 and BEST-AV2 is either LED display or LCD display of modes, power setting, timer, and reaction indications. The

BEST-AV2 devices have the same output specifications and technology as well as the same indications for use as the Rx devices in K062641.

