### **Sample size estimation:**

The estimated number of study subjects is 40. The sample size for the short-term effect (immediate changes in skin perfusion) was estimated to achieve 85% power when comparing to baseline values, using assumed rates of 50% and 10% improvement, respectively. A two-sided test of results in evaluable subjects (qualified for analyses of efficacy on immediate changes on skin perfusion) will provide the specified power at a 5% significance level. Sample size calculations resulted in a requirement for a total of 27 subjects. The sample size for long term benefit was estimated based on our previous study (Najafi et al, Diabetes Sci & Tech, 2017) in which effectiveness of daily use of electrical stimulation to improve balance was examined using a randomized controlled trial model. An effect size of greater than Cohen’s  $d=1.35$  was observed for improvement of mobility post plantar electrical stimulation intervention. In this study we will use a power of 80%, two –tailed t-test, and alpha level of 5% to observe a significant improvement in the intervention group receiving active stimulation compared to sham group (with nonfunctional stimulator), 18 subjects per group is required. Assuming a 10% drop out, the estimated sample size would be 20 subjects per arm. We recognize that this sample size may not be sufficient to validate all primary and secondary outcomes, but would be sufficient to estimate trend and estimate the sample size for follow up study. Upon approval of the sponsor, availability of budget, and based on initial results (first 20 subjects), the sample size may be increased as well.

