## Study Tasks:

Medical History: The presence of diabetes will be determined based on American Diabetes Association criteria. This will include: duration and type of diabetes, type of diabetes medication (insulin, oral, combination therapy, diet), previous history of foot ulcers, amputation (toe, foot), lower extremity bypass, lower extremity angioplasty, Coronary artery bypass surgery, cardiac angioplasty, arthritis, liver disease, osteoporosis, malignancy, and bone tumors. We will measure height and weight to determine body mass index (BMI). We will evaluate glycated hemoglobin, albumin and prealbumin at baseline. We will confirm PAD by measuring ABI.

Social Factors: We will evaluate the following factors: marital status, years of education, type of work, tobacco history (pack years, current smoker, current use of chewing tobacco, previous smoker, no tobacco history), drug history (current, previous history, or no history), and alcohol history.

BEST Therapy: The participant will be given an active Tennant Biomodulator PRO ® by the research staff. They will place the pads on the plantar area of the foot and provide therapy for one hour. At the end of the visit, the research staff will provide an active or sham Tennant Biomodulator ® to the participant for in-home therapy. The participant will have the ability of increasing/decreasing the intensity of the therapy with the Tennant Biomodulator ®. At each visit, the research staff will provide AA batteries to the participant for the device.

Peripheral Neuropathy: Neuropathy and its severity will be assessed using vibratory perception threshold (VPT) at the affected side. VPT will be evaluated at the distal great toe and fifth metatarsal head using a Biothesiometer.

Vascular Assessment: We will assess perfusion of the macro-circulation with arterial Doppler studies and microcirculation with Skin Perfusion Pressure measurements (SPP) at the affected side. We will use the SensiLase system (Väsamed) to measure SPP in mmHg. Ankle Brachial Index (ABI) will be also measured in the case of compressive vessel and if it was feasible (e.g. in non-hemodialysis patients) on the affected side. Additionally, we will use HyperView Imaging (HyperMed Imaging, Inc., TN, USA) or Kent Camera (Kent Imaging Inc., Calgary Canada) for surface tissue oximetry measurement.

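### Aim 1 has no concurrent control for the one-hour session, so it can show a change in perfusion during the session but cannot attribute it to stimulation

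*Protocol*

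**What the plan says.** Under Study Design, Aim 1 has one group: "We will recruit 40 eligible subjects". Its treatment is the same for all: "They will receive lower extremity electrical stimulation (at the shin level) for duration of approximately one hour using the Tennant Biomodulator Pro device". Perfusion is read at the start, about halfway and at the finish. The hypothesis is "One-hour use of lower extremity electrical stimulation therapy will increase tissue perfusion".

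Study Tasks (BEST Therapy) confirms that the clinic device is active for everyone: "The participant will be given an active Tennant Biomodulator PRO ® by the research staff". Allocation matters only afterwards: "At the end of the visit, the research staff will provide an active or sham" unit for use at home.

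Sample size estimation says the short-term effect was "estimated to achieve 85% power when comparing to baseline values", with improvement rates of 50% and 10%, a two-sided 5% level and 27 subjects in total. Statistical analysis applies repeated measures within each group, adjusted for age and BMI, and says a similar test serves the short-term effect. The SAP has time and time-by-group terms but does not mention the one-hour response.

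Randomisation 1:1 to active or sham (20 per group) belongs to Aim 2. Randomization & Blinding supports the blind partly by saying that enrolled patients have no previous experience of how stimulation feels.

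**The concern.** The hypothesis is about what stimulation does, but the comparison is between two times in the same treated people. Settling into the room, posture, repeated readings and regression to the mean can all move a perfusion reading over an hour, and they act on every participant together with the device. Adjusting for age and BMI does not remove them. The SAP's time-by-group term does not help either: both allocated groups receive the active device in that hour, so for Aim 1 it would compare active with active.

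At stake is the interpretation of a significant Aim 1 result, which would be reported as a device effect when the design supports only a statement about change over the session. There is also a side effect on Aim 2: participants later given a sham unit have already had an hour of active stimulation.

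**Working it through.** **1. The plan's own figure.** Inputs from Sample size estimation: rates 0.50 and 0.10, power 85%, two-sided 5%, 27 in total. The formula is not named. Two routes give 27.

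- Paired exact McNemar test, assuming independent marginal rates. Discordant probabilities are 0.50 × 0.90 = 0.45 and 0.10 × 0.50 = 0.05. Power is about 84% at n = 26 and 86% at n = 27, so 27 in total.
- Two independent proportions. n = [1.960·√(2 × 0.30 × 0.70) + 1.036·√(0.25 + 0.09)]² / 0.40² = 21.96, so 22 per arm. With continuity correction, (21.96/4)·[1 + √(1 + 4/(21.96 × 0.40))]² = 26.7, so 27 per arm, or 54 in total.

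Whether 27 is a paired total or a per-arm number cannot be settled. The words about comparison with baseline fit the paired reading.

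**2. What the before-after test does if the device is inert.** The documents give no SD and no figure for change without stimulation, so drift δ, in SD units of the within-person change, is an assumption shown over a range. The repeated measures analysis is simplified to a paired t-test. The chance of a significant increase is P(T > t₀.₉₇₅), with T noncentral t on n − 1 degrees of freedom and noncentrality δ√n. For n = 40 the critical value is 2.023.

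| Drift δ | δ√40 | n = 40 | n = 27 |
|---|---|---|---|
| 0 | 0 | 2.5% | 2.5% |
| 0.1 | 0.63 | 9% | 7% |
| 0.2 | 1.26 | 23% | 17% |
| 0.3 | 1.90 | 46% | 32% |
| 0.4 | 2.53 | 69% | 52% |
| 0.5 | 3.16 | 87% | 71% |

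A randomised comparison would keep its nominal 5% two-sided level at every row, because drift common to both arms cancels.

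**3. The same check on a responder scale.** Suppose improvement were tested against a fixed 10%. With 40 subjects the exact rule is 9 or more responders (one-sided size 1.5%). If the true rate without stimulation were 15%, 20% or 30%, the test would be positive 14%, 41% or 89% of the time.

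**4. What a concurrent sham would cost in sensitivity.**

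- Continuous change, 80% power: the before-after test on 40 detects 0.45 SD (0.45 × √40 = 2.85). A 20 v 20 comparison detects 0.91 SD (0.91 × √(20/2) = 2.88; critical t on 38 df = 2.024).
- For a difference of 0.45 SD, 20 v 20 has noncentrality 0.45 × √10 = 1.42 and power 28%.
- If 50% v 10% is read as active v sham (an assumption; the protocol ties these rates to baseline), exact power at 20 v 20 is 84% by Pearson chi-square and 74% by Fisher. Reaching 85% by the formulas in step 1 takes 2 × 22 = 44 or 2 × 27 = 54 subjects.

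**The case against.** The strongest reply is that Aim 1 is openly a short-term, supplementary aim. It is not among the primary outcomes listed for Aim 2, and perfusion is also assessed under randomised allocation over four weeks. The sample size section itself says the trial may do no more than estimate trends. All this stands and limits the damage. It does not repair the Aim 1 hypothesis, because a four-week comparison does not control a one-hour response.

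The 10% rate may be the plan's allowance for spontaneous improvement. If so, no data in the trial estimate it, the Statistical analysis section does not test against it, and step 3 shows how sensitive such a test is to it.

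A reader might infer that the false-positive percentages describe this trial. The documents do not support that: they give no drift, SD or direction. Sitting or lying with the foot raised is specified only for home sessions, so an hour of rest in clinic is itself inferred. A downward drift would hide a device effect.

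A reader might also infer that a sham control is ready to hand and nearly free. Aim 1 names the PRO device, while sham is described only for the home model: "the research staff will provide an active or sham Tennant Biomodulator ® to the participant for in-home therapy". The Study Device section does say "BEST-AV2 devices have the same output specifications and technology" as the prescription home family, but it also lists over 50 modes and programmable settings for the PRO against four modes for the home unit. Using the assigned home unit would change the device under study; keeping the PRO would require a sham PRO. The loss of power is real, and 74% is not close to 85%.

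**Conclusion.** The point holds in a limited form. All participants receive active stimulation, the test is against baseline, and nothing runs alongside as a control, so the causal Aim 1 hypothesis is not testable as designed. This follows from the text and needs no assumption. Its size does: with 40 subjects and an inert device, the chance of declaring an increase runs from 9% at 0.1 SD of upward drift to 87% at 0.5 SD, against a nominal 2.5% in that direction.

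The documents do not show that drift occurs, and the point does not touch Aim 2's randomised perfusion comparison. Nor do they show that the sham group receives active stimulation at every clinic visit. The Schedule of Events lists BEST Therapy at baseline and at later visits, and Study Tasks calls the clinic device active, but Study Tasks does not say whether that covers the later visits. What is clear is that the sham group has an active baseline hour, which sits badly with the statement that patients do not know the sensation.

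**What to change.** **Change to make.** In the protocol, reword the Aim 1 hypothesis (Study Design) and the short-term analysis (Statistical analysis) to *change in perfusion during a one-hour session*, and state that no attribution to stimulation will be made. This costs wording only: no added patients, visits or equipment.

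**Option, if the sponsor wants a causal claim.** Randomise before the baseline hour, run that hour as active or sham, and compare the change in skin perfusion pressure between arms, adjusted for the pre-session value. The amendment should state the costs:

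- a sham PRO, or use of the home unit in clinic in place of the device Aim 1 names;
- lower sensitivity: 0.91 SD detectable at 80% power with 20 v 20, against 0.45 SD before-after;
- power of 74% (Fisher) to 84% (chi-square) if 50% v 10% is taken as active v sham, or 44 to 54 subjects to restore 85%.

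**Reconcile separately.** The Schedule of Events and Study Tasks (BEST Therapy) must be reconciled with the claim in Randomization & Blinding that patients are new to the sensation. The protocol should state which clinic sessions are active for the sham group, and the blinding argument should take account of the active baseline hour.

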### **Schedule of Events**

Visit	Baseline assessment	Follow up					
		#	0	1	2	3	4
Consent & HIPPA forms	X						
Screening (inclusion and exclusion criteria)	X						
Medical & Surgical History	X						
Gram Stain	X					X	
Neuropathy assessment (VPT)	X		X			X	
Immediate Skin Perfusion Pressure Response after one hour of BEST Therapy	X						
BEST Therapy	X	X	X	X	X		
Optional assessments		X				X	
Upper Extremity Test	X					X	
WiFi wound classification	X	X	X	X	X		
Vascular Assessments (SPP and HyperView/Kent Imaging)	X					X	
Wound Photos	X	X	X	X	X		
Thermal Images	X		X			X	
Wound Care (standard of care)	X		X			X	
Adverse Events Reporting	X	X	X	X	X		
Pain Questionnaire (VAS)	X	X	X	X	X		
Heart Rate Variability	X	X				X	
Health Questionnaires (MOCA, FESI, CES-D, PSQI, TSFI, Promis Global)	X					X	
Device Acceptability Questionnaire						X	
Phone Interview							X

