Gram Stain: Bacteria levels will be assessed by collecting a samples and ordering a Gram Stain assessment, which provides an estimate of number of bacteria in the wound. A sample will be collecting before treatment and at 4 weeks.

Wound photo: A digital photo/video will be taken to record wound size.

Thermal Image: A Thermal camera will be used to obtain an image of the wound and observe inflammation.

Definition of Healed Wounds: A wound will be considered “healed” when it is fully epithelialized with no drainage. Only patients with non-infected wound will be recruited. *Infection* will be defined as a patient with three of six clinical signs of infection (erythema, heat, edema, pain, loss of function, purulence) or leukocytosis. We will use the Infectious Diseases Society of America’s Diabetic Foot Infection guidelines to stratify the severity of infection. This guideline stratifies infections into four categories (none, mild, moderate, and severe) based on practical clinical and laboratory findings. Our group has shown this system to be predictive of morbidity.

Health Questionnaires: Quality of Life, Frailty Status, Fear of Falling, Sleep Quality, Depression and Mental Status and Device Acceptability: To evaluate functional status we will use well-accepted questionnaires, PROMIS for Quality of Life, Sleep Quality questionnaire (PSQI), MOCA for cognitive assessment, FES-I for fear of falling, CES-D for depression and TSFI for frailty status. During the last visit, we will ask an acceptability questionnaire.

Upper Extremity Assessment: Investigators will measure the participant's arm motion using a wearable sensor (LegSys, Biosensics LLC, MA USA). This sensor will be placed around the wrist. While being at a comfortable position, the participant will be asked to flex and extend their arm for 20 seconds at a fast speed. They will also be asked to repeat this task but counting backwards as the participants flex and extend their arm (dual task). (Measurement will be done at baseline and visit 4)

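### H3 (plantar sensation, a primary outcome) and the efficacy parts of H4 are worded as improvement in the active arm, and neither document says that the active-versus-sham contrast decides them

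*Protocol*

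**What the plan says.** H2 to H4 here are the Aim 2 hypotheses in the Protocol's Study Design. The Purpose section numbers a different list.

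- **Outcomes.** "The primary outcomes include changes in speed of wound healing and changes in plantar sensation". Sensation is measured by VPT. Patient-reported outcomes, mobility and adverse outcomes are secondary.
- **H2** names its comparator: "Weekly speed of wound healing would be higher in the active group compared to the shame group".
- **H3** does not: "Plantar sensation is improving in the active group in response to active therapy".
- **H4** does not either: "Patient-reported outcomes and other secondary outcomes will be improved in the active group".
- **Sample size estimation** plans Aim 2 "to observe a significant improvement in the intervention group receiving active stimulation compared to sham group".
- **Protocol, Statistical analysis** uses repeated measures ANOVA, replaced by a linear mixed model to handle missing data, for the intervention effect arm by arm. It defines long-term benefit as change in primary and secondary outcomes after 4 weeks, gives a between-group Cohen's d, and compares adverse events between groups by chi-square.
- **SAP** plans comparisons of control and intervention means, a between-group Cohen's d for primary and secondary outcomes, and a mixed model (GEE if non-normal) with both a within-group time effect and a time × group effect.
- **Study Tasks**, on the H3 measure: "VPT will be evaluated at the distal great toe and fifth metatarsal head using a Biothesiometer". No rule says which site counts, or whether the two are averaged.

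**The concern.** The sham arm is there so that change can be attributed to stimulation. A before-after change in the active arm alone cannot be attributed in that way, because it also contains whatever would have happened under sham. H3 read literally is satisfied by that before-after change, and the planned model will produce a p-value for it. If the active arm's VPT improves and the time × group result is unremarkable, the documents would let H3 be reported as confirmed on a primary outcome.

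The protocol's own rationale offers a possible shared route. Study Tasks has participants receive an hour of active stimulation through plantar pads in clinic before an active or sham home device is issued, so both arms get it. Background says stimulation could improve mobility and balance through enhanced plantar sensation. Whether any such effect lasts to week 4 is not stated. Aim 1 describes stimulation at the shin, so the pad placement also needs reconciling.

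**Working it through.** **1. Which contrast does each place support?**

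| Place | Contrast | Decides H3 or H4? |
|---|---|---|
| Study Design, H3 and H4 | active arm only | as worded, yes |
| Sample size estimation | active v sham | not tied to H3 or H4 |
| Protocol, Statistical analysis: ANOVA / mixed model | arm by arm | not stated |
| Protocol, Statistical analysis: Cohen's d | between arms | effect size only |
| Protocol, Statistical analysis: adverse events | between arms | settles that part of H4 |
| SAP: means and Cohen's d | between arms | not stated |
| SAP: mixed model or GEE | time, and time × group | neither ranked |

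Sample size estimation and Statistical analysis, read together, point to sham as the intended comparator. No sentence makes it the deciding one.

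**2. Inputs.**
- From the documents: 18 evaluable per arm; two-sided 5%; VPT at baseline, a middle visit and the last visit. The dropout step reproduces: 18/(1 − 0.10) = 20. The 18 does not follow from d = 1.35 at 80% power (a t-test needs 10 per group). That is a separate matter, and 18 is used here only as the evaluable number.
- Assumed, because the documents give neither a shared VPT change nor its variability: no device effect; the same change δ in both arms, 0 to 0.3 SD of change; compound symmetry with correlation over time of 0.5 or 0.7; normal, complete data; half the change at the middle visit; no covariates; one VPT measure.

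**3. Simple check: one-sample t-test on change in the active arm.** Noncentrality = δ√18 = 0, 0.424, 0.849, 1.273; df = 17; critical value 2.110. The probability of a significant favourable result is 2.5, 5.9, 12.3 and 22.4%.

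**4. Mixed model with three visits.** Residual df = (36 − 2) × (3 − 1) = 68; critical value 1.995.
- Within-arm week-4 contrast: noncentrality δ√18, as above.
- Between-arm week-4 contrast: noncentrality (δ − δ)/√(2/18) = 0 for every δ.

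Simulation with 60,000 trials per setting gives:

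| Assumed shared change (SD of change) | Within-arm significant, favourable | Between-arm favours active | Within-arm yes, between-arm no |
|---|---|---|---|
| 0 | about 2.5% | about 2.5% | about 1.6% |
| 0.1 | about 6% | about 2.5% | about 4.8% |
| 0.2 | about 13% | about 2.5% | about 11% |
| 0.3 | about 24% | about 2.5% | about 22% |

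**5. Which model term is the between-arm difference?** This depends on how baseline is handled. If baseline is one of the responses, the week-4 time × group contrast is the difference in change from baseline. If baseline is a covariate and removed from the responses, time × group only asks whether the effect differs between the middle visit and week 4. Simulating that second model (18 per arm, correlation 0.5, a true effect of 1 SD at both visits), the week-4 group difference is significant in about 90% of trials and the literal time × group term in about 5%. The deciding term must therefore match the model.

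**The case against.** The strongest reply is that the documents already point to sham. The trial is randomised, double-blind and sham-controlled. Long-term benefit is sized against sham and defined elsewhere as change in the primary and secondary outcomes. Sample size estimation itself speaks of improvement in the intervention group and then completes the phrase with sham, so H3 and H4 may be shorthand. The SAP adds group comparisons, and the only effect size it plans for these outcomes is between groups. All of this stands as evidence of intent. It does not supply a decision rule, and the arm-by-arm and time effects remain in the plan unranked. The caveat that the sample may be too small for all outcomes does not choose between contrasts.

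The illustration also has limits. At zero shared change the two tests have the same favourable error rate. The figures cover only the mixed model with normal, complete data. VPT is read on a bounded 0–50 V scale and may go to GEE, where an uncorrected robust test at 18 per arm gave about 3.3% between arms rather than 2.5%.

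A reader might infer two stronger things, and the documents support neither. One is that no active-versus-sham analysis of VPT is planned; the SAP's time × group effect and group comparisons contradict that. The other is that VPT is known to improve in both arms; no passage says so, and the clinic session is only a possible route.

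**Conclusion.** The point holds as a gap in the decision rule, and it should be closed because it touches a primary outcome. The between-arm analysis exists and is probably what was meant, but H3 and the efficacy parts of H4 can be declared met on a within-arm change. Adverse events are not affected. The textual finding rests on no assumption. Its consequence does: it ranges from none, if nothing is shared with sham, to roughly one trial in four at a shared change of 0.3 SD, under the conditions listed in the working. No rate is claimed for H4 as a whole or for the GEE route. Multiplicity across the two primary outcomes is a separate matter and plays no part here.

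**What to change.** - Restate H3 and the efficacy parts of H4 as active-minus-sham differences, as H2 already is.
- State in the Protocol's Statistical analysis and in the SAP that the between-arm difference at week 4 decides them. If baseline stays among the responses, with or without equal baseline means imposed, this is the week-4 time × group contrast. If baseline is a covariate and removed from the responses, it is the group difference at week 4, not the time × group term.
- Name one VPT site, or the mean of the two, as the H3 measure.
- Report within-arm changes as descriptive, with confidence intervals.

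**Cost:** wording in Study Design, Statistical analysis and the SAP, with no extra participants or measurements. The downside is that some positive statements based on the active arm alone are lost.
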